The proposed prospective investigation will be designed as a non-inferiority study. Study sites will identify and recruit children and/or adults with known CD that are undergoing routine clinical MRE examinations for staging / restaging of intestinal inflammation, follow-up of luminal narrowing / stricturing disease, or follow-up of patients with known internal penetrating disease. Enrolled participants will 1) undergo a dedicated research abbreviated MRE examination within ± 10 days of their clinical MRE, at the convenience of the participant, and 2) participants will be surveyed about their preference / patient experience for the standard-of-care vs. abbreviated MRE protocol. Furthermore, we will ask a series of “trade-off” questions to understand patients’ willingness to tolerate a loss of examination performance to improve patient experience. These tradeoff questions will use a survey method called a discrete choice experiment (DCE), which is a technique based on behavioral economic theory that asks respondents to make a series of discrete choices between medical care strategies.

The parents/guardians of pediatric participants (10-17 years of age) also will receive a similar survey to understand their perspective, and how it may differ from their children.

Board-certified, fellowship-trained radiologists will review both the standard-of-care and abbreviated MRE examinations in separate sessions to document the presence and severity of small bowel inflammation; the presence and features of stricturing disease (and penetrating disease, if present) also will be recorded. The diagnostic performance of the abbreviated MRE protocol will be determined for individual readers and all readers combined, using the standard-of-care protocol as reference standard.

At the end of the proposed study, we will have shown if a patient-centric, noncontrast, abbreviated MRE protocol can be used to evaluate children and adults with CD as well as if such a protocol offers an improved patient experience. If successful, such an abbreviated protocol could enable more frequent patient follow-up imaging, with more individualized patient management and improved patient outcomes, including more frequent transmural healing. Such an abbreviated protocol also could be used in the research setting to assess the effectiveness of candidate anti-inflammatory and anti-stricture (i.e., anti-fibrotic) therapies.

5. DURATION:

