The survey will be administered on a tablet/ipad that will be supplied by a study team member. The survey will present hypothetical scenarios describing an MRE strategy. Participants will be asked to make a choice between two separate MRE imaging strategies with defined characteristics (see figure immediately below as an example). Characteristics will relate to multiple domains, including IV contrast, oral contrast, side effects such as nausea and vomiting, cost, exam time, and exam diagnostic performance. The survey will describe the attributes and walk respondents through a practice question to introduce the concept of discrete choice tasks.

If you had to choose an exam for follow-up, which exam would you prefer?		
	Option A	Option B
Accuracy	90%	80%
Exam time (minutes)	45	10
Out-of-pocket cost	\$500	\$400
IV contrast required	Yes	No
Please select one		
If you had to choose an exam for follow-up, which exam would you prefer?		
	Standard MRE	
	Abbreviated MRE	
	I don't know	

Study Chronology:

Procedure:
Telephone NPO Consent*
Informed Consent
Medical History
Clinical MR
Abbreviated Research MRE**
Patient Experience and Preference Survey (Discrete Choice Experiment)***

*Using the phone script, verbal consent will be obtained prior to the research MRI study to confirm participants will not eat or drink for 4 hours prior to the research MRE.

**Research MRE may occur ± 10 days from Clinical MRE.

*** Once the research MRE and the clinical MRE are completed, participants and a parent of a participant age 10-17 will be asked to complete a questionnaire. This may require a second research encounter depending upon whether the research MRE or clinical MRE is performed first.

The participants must be nil per os (NPO) 4 hours prior to both the clinical and research MRE exams. If a participant is not NPO 4 hours prior to their MRE exams and is able to reschedule within window (if applicable) the participants visit(s) will be rescheduled.

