For the dedicated research imaging visit, enrolled participants will undergo dedicated research, abbreviated MRE examination within ± 10 days of their clinical MRE, at the convenience of the participant. Research MRE examinations will be standardized across sites, while clinical MRE examinations will be performed at each site using standard-of-care protocols. Clinical MRI examinations will be performed on both 1.5-T and 3-T MRI scanners from all major scanner manufacturers (i.e., GE HealthCare, Philips Healthcare, and Siemens Healthineers).

Research MRE examinations will be performed on dedicated research MRI scanners which will facilitate participant scheduling. 3-T scanners will be used at Mayo Clinic (Philips Healthcare) and NYU Langone Health (Siemens Healthineers). 1.5-T and 3-T scanners will be used at CCHMC (Philips Healthcare). We plan for these examinations to be performed in less than 15 minutes of scan time, on average.

For research MRE examinations, patients will ingest a standardized volume (weight-based, approximately 20 ml/kg, maximum of 1500ml) of water during the 45-minute period prior to their scheduled imaging time. At $\sim 10\%$ participant recruitment, research MRE examinations will be reviewed to ensure that water is providing adequate bowel distention and image quality.

During and after each research MRE examination, the research coordinator conducting the study visit will document any patient discomfort / distress such as, nausea, vomiting, etc.

Pertinent participant characteristics, including demographics, relevant clinical and laboratory data, and most recent MRI or CT comparison imaging (both reports and DICOM images) will also be obtained at the time of the research visit.

Fellowship-trained, board-certified radiologists from multiple institutions will independently review both the clinical standard-of-care and research abbreviated MRE examinations in separate sessions using a cloud-based image viewer to document the presence and severity of intestinal inflammation. Prior clinical MRE or CT examinations may be made available for comparison. The diagnostic performance of our abbreviated MRE protocol will be determined for individual readers and all readers combined, using standard-of-care clinical MRE examinations as reference standard.

Patient Preference Survey

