The diagnostic performance of our abbreviated MRE protocol will be determined for individual readers and all readers combined, using standard-of-care clinical MRE examinations as reference standard. The presence of clinically meaningful (i.e., moderate-severe) active intestinal inflammation will serve as our primary outcome of interest. These analyses will be performed at the overall examination and individual bowel segment level. Sensitivity, specificity, accuracy, positive predictive value, and negative predictive value will be calculated, with 95% confidence intervals. In addition, the global and individual bowel segment sMaRIA scores will be compared and correlated between clinical and research examinations using Mann-Whitney U tests and Spearman rank-order correlation. The diagnostic performance of the abbreviated MRE protocol for detecting luminal narrowing, stricture disease, internal penetrating disease, and perianal disease will also be calculated, again using clinical MRE examinations as the reference standard. Finally, Fleiss' kappa statistics will be used to evaluate inter-reader agreement for the different imaging features documented. The above results may be compared between readers without and with access to prior MRE or CT imaging when interpreting both the research and clinical MRE examinations.

Survey Analysis:

The analysis will be conducted in STATA, a statistical program. The unit of analysis for all analyses will be the individual participant. We will obtain data on respondent demographics and health characteristics, from baseline questions in the survey. We will summarize continuous outcome measures using means and standard deviations. We will compare continuous outcome measures

across groups (e.g. low versus middle versus high income levels, parent education level, proportion using a CGM) and test for statistical differences between groups using t-tests. We will summarize categorical outcome measures using frequencies and proportions and test for statistical differences between groups using chi-square tests. All statistical analyses will be conducted in Sawtooth Software and Stata (version 17).

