There are minimal risks associated with this study. The primary risk relates to research MRI safety issues, such as burns and projectile-related injury. Standard-of-care MRI safety and screening practices will be performed by appropriately trained individuals/technologists at each site. The MRI scanner creates noise in the process of image acquisition. To mitigate this, study participants will be provided with hearing protection (ear plugs) per standard clinical practice.

Loss of confidentiality is another potential risk. This risk will be mitigated through the privacy and confidentiality measures described below.

While there are no known risks to noncontrast MRI during pregnancy, patients that are known to be pregnant or possibly pregnant will not be enrolled out of an abundance of caution.

Adverse events occurring during study participation will be documented by study personnel and reported to the IRB, as required.

13. RISK/BENEFIT ANALYSIS:

Overall, the proposed study has minimal risk, and the potential benefits of a future abbreviated clinical MRE examination that would allow more frequent, faster, potentially lower cost assessments are considerable. Thus, the risk/benefit ratio is favorable.

14. DATA SAFETY & MONITORING:

No DSMB will be assembled, as the proposed study is minimal risk, has no significant impact on patient care, and is not being used to make medical decisions. A study coordinator will be present for the duration of the participant's research MRI visit. Any adverse events that may occur will be documented by the coordinator and assessed by a study team medical doctor for severity and relatedness to the study. Investigators will closely monitor data and participants to immediately identify any potential risks and adverse events which will be reported to the IRB by the study team in a timely manner, as required.

15. PRIVACY and CONFIDENTIALITY:

All study data will be handled in a HIPAA-compliant manner. Paper records will be stored in secure, locked offices and cabinets. Electronic records will be password-protected. Study data will be entered into a HIPAA-compliant database, such as REDCap. Imaging data will be stored and reviewed on a HIPAA-compliant cloud platform; all PHI will be removed from imaging data except for date of encounter.

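### The reading rule in Section 8 leaves room for carry-over between a participant's two reads, which would mostly favour non-inferiority

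*Protocol*

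**What the plan says.** Protocol Section 4 says of the readers that they "will review both the standard-of-care and abbreviated MRE examinations in separate sessions". Section 8 repeats the rule and adds independence and the platform: they "will independently review both the clinical standard-of-care and research abbreviated MRE examinations in separate sessions using a cloud-based image viewer". Neither section states a minimum interval, a reading order, a shuffle of cases, or masking of the participant's other scan.

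Three further statements bear on whether a reader could link the two scans:

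- Section 15, on images stored and reviewed on the cloud platform: "all PHI will be removed from imaging data except for date of encounter".
- Section 8, Study Chronology: "Research MRE may occur ± 10 days from Clinical MRE".
- Section 8, on comparison imaging: "Prior clinical MRE or CT examinations may be made available for comparison". The same section has the most recent MRI or CT collected at the research visit, both images and reports.

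On what the reads are used for, Section 4 states: "The proposed prospective investigation will be designed as a non-inferiority study". Section 9 states: "The presence of clinically meaningful (i.e., moderate-severe) active intestinal inflammation will serve as our primary outcome of interest". Performance is to be "determined for individual readers and all readers combined, using standard-of-care clinical MRE examinations as reference standard". The protocol does not say whose reading of the clinical MRE is the reference: the reader's own, a consensus or majority read, or the clinical report.

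**The concern.** The abbreviated scan is scored by how well it reproduces the clinical scan, and there is no external reference. Information that passes from one read to the other therefore enters the primary result directly. Scan type cannot be masked, because the sequence table in Section 8 gives post-contrast series to one examination and a cine series to the other. What can be masked is the link to the same participant's other scan, and the protocol protects that link only by separate sessions. Two sessions on one day would comply.

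If a reader recognises a participant and leans on the other read, the two reads move together. In a study whose hypothesis is non-inferiority, that error mostly runs in the hypothesis's favour. It cannot be removed once the reads have been done, so it has to be prevented in the reading procedure.

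**Working it through.** The protocol gives no figure to reproduce on this point. The check has three parts: routes to linkage, direction, and an illustration of size.

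**1. Routes to linkage**

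*Encounter date.* Inputs: about 100 participants per site at three sites (Section 6), 36 months of recruitment and imaging (Section 5), and a ±10-day window, taken as 21 days (Section 8). Assumption: uniform accrual. The period is 36 × 30.4375 = 1,095.75 days. Expected number of other participants within the window of a given scan:

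- same site: 99 / 1,095.75 × 21 ≈ 1.9
- all sites: 299 / 1,095.75 × 21 ≈ 5.7

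A visible date would narrow the match to a few participants but would not identify the pair on its own. Anatomy could complete the match, since the stricturing and penetrating disease recruited under Section 6 can look distinctive.

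*Prior imaging.* Section 8 allows either scan to come first. If the clinical MRE comes first, it can be the most recent MRI when comparison images and reports are collected at the research visit. Nothing in Section 8 or Section 9 excludes it from the priors shown to readers. In that case the reference examination could be on display during the abbreviated read. Showing the same older prior in both sessions could also link the pair.

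**2. Direction**

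- Clinical scan read first: recall brings its content into the abbreviated read. This mostly raises agreement, whichever reference is used.
- Abbreviated scan read first: agreement rises if the reference includes that reader's own later clinical read. If the reference is the clinical report, this order adds no such bias.
- If the reference is a consensus read or the clinical report, a reader who repeats an error from their own earlier read can lower measured performance.

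The effect is therefore mostly, but not always, upward.

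**3. Illustration of size**

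Let A be agreement under independent reading and r the share of pairs in which the second read copies the first. Take the reader's own clinical read as the reference. Copied pairs agree with certainty and the others agree at rate A, so observed agreement is r + (1 − r)A = A + r(1 − A). Both A = 0.85 and r are assumptions.

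| r | Observed agreement |
|---|---|
| 5% | 0.85 + 0.15 × 0.05 = 0.8575 |
| 10% | 0.85 + 0.15 × 0.10 = 0.865 |
| 20% | 0.85 + 0.15 × 0.20 = 0.88 |
| 40% | 0.85 + 0.15 × 0.40 = 0.91 |

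The gain runs from under 1 point to 6 points. The formula assumes that copying is unrelated to whether the pair would have agreed anyway. If the scans most easily recognised are also the easiest to read, the gain is smaller.

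The same formula applied to sensitivity shows what could follow for a non-inferiority conclusion. Assume a bound of 0.80, a true sensitivity exactly at that bound, and success when the Wilson 95% lower limit exceeds it. The exact binomial probability of wrongly concluding non-inferiority is then:

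| Assumed positives (of 300) | r = 0 | r = 10% | r = 25% |
|---|---|---|---|
| 90 (30%) | 1.9% | 5.3% | 19.0% |
| 150 (50%) | 2.2% | 8.0% | 33.2% |

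The bound, the counts of positives and the values of r are all assumed.

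**The case against.** The strongest reply is that this is largely silence. Independent review in separate sessions is a correct, if brief, statement that contradicts nothing, and washout, case order and viewer set-up may sit in a reader manual that is not shown. That is fair as to detail. It does not dispose of the point, because the protocol itself sets the reading rule, twice, at a level that same-day sessions would meet. This is reading conduct, not an analysis choice that would normally be left to an SAP.

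Several stronger readings are tempting, and the documents do not support them:

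- *That agreement will be inflated.* It is a risk. Whether it occurs depends on how the reads are run, and its effect depends on the unstated source of the reference read.
- *That the retained dates identify the pairs.* Section 15 is a privacy clause. It does not say that readers see the date, and about 2 other same-site participants, or about 6 across sites, would be expected within the window.
- *That the gain is several points.* The larger values need assumed copying rates of 20% to 40%. At 5% the same formula gives under 1 point.
- *That readers will meet cases they have already reported clinically.* Section 8 says only that readers come from multiple institutions. Overlap is neither stated nor excluded.

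The remedy also has limits. Keeping readers off particular cases can leave unequal numbers of ratings per case, which complicates Fleiss' kappa and the combined-reader analysis in Section 9. Removing all date information would hinder comparison with genuine priors.

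**Conclusion.** The concern holds as a weakness in the reading rule. The stated safeguards do not prevent one read from influencing the other, and the provision on prior imaging leaves open that the reference scan itself is shown. Where carry-over acts, it mostly favours non-inferiority. Its size is unknown: the 0.86 to 0.91 range and the error rates above are illustrations, and they rest on assumed agreement, copying rates, bound and prevalence, with the reader's own clinical read as the reference. The change is worth making before reading starts, because it is cheap then and impossible afterwards.

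**What to change.** In Section 8, specify that:

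1. The two scans of a participant carry separate random viewer codes.
2. Encounter dates are hidden from readers and kept in the database to check the ±10-day window. Relative dates may be supplied for true priors.
3. Each session presents one scan per participant, in random case order, with scan type counterbalanced across readers and sessions.
4. A minimum washout separates a reader's two reads of the same participant. Four weeks is an example, not a figure from the documents.
5. The paired examination and its report may never serve as a prior.
6. Where feasible, readers are not assigned cases they reported clinically; where this cannot be avoided, those reads are flagged for a sensitivity analysis. Flagging avoids unequal numbers of ratings per case.

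Stating whose read of the clinical MRE is the reference would settle how far any remaining carry-over could matter.

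The cost is viewer configuration, a reading schedule and a somewhat longer reading calendar, which fits within the roughly 12 months that Section 5 allows for analysis.

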Patients will be recruited, enrolled, and imaged over a 36-month period. Data analysis will begin approximately month 30 and will require approximately 12 months to complete.

6. SELECTION & RECRUITMENT OF PARTICIPANTS:

Study sites (CCHMC, Mayo Clinic, and NYU Langone Health) will identify and recruit children and/or adults with known CD that are undergoing clinical MRE examinations for staging / restaging of intestinal inflammation, evaluation of known or suspected luminal narrowing / stricturing disease, and/or evaluation of known or suspected internal penetrating disease. CCHMC will recruit predominantly pediatric CD patients, while Mayo Clinic and NYU Langone Health will recruit

predominantly adult CD patients. Approximately one hundred participants will be enrolled and imaged at each site. Participants need to be English speaking in order to follow breath-hold commands and to complete the preference and “trade-off” surveys.

Inclusion Criteria:

Subjects will be recruited for our study using the following inclusion criteria:

- Established Crohn's disease diagnosis in patients 10 years of age and older
- Undergoing clinical MRE examinations for any reason(s) below:
 - Staging / restaging / follow-up of intestinal inflammation
 - Evaluation of known or suspected luminal narrowing / stricturing disease
 - Evaluation of known or suspected internal penetrating disease

Exclusion Criteria:

- Undergoing initial imaging for suspected CD where the diagnosis of CD has yet to be definitively established
- New CD diagnosis, undergoing baseline imaging
- Isolated colonic disease
- Known or suspected pregnancy
- Contraindication to MRI (e.g., due to certain implanted medical devices)
- Ileostomy or prior ileal resection
- Less than 10 years of age
- Unable or unwilling to follow imaging procedures
- Non-English speaking

7. PROCESS OF OBTAINING CONSENT:

Only outpatient CD patients receiving clinically indicated imaging will be recruited for this study. Participants will be screened in advance of enrollment by study personnel to determine baseline eligibility for participation. Each subject will be informed that participation in the study is completely voluntary and that he/she may withdraw from the study at any time and that withdrawal of consent will not affect his/her subsequent medical treatment or relationship with the treating physician.

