We will estimate preferences for imaging using a mixed logit model (i.e., a random coefficient logit model), a statistical model designed to analyze discrete choices. Variation in preferences related to health and demographic characteristics will be captured through specification of covariates in the model. The coefficients of each attribute in the mixed logit model represent estimates of the probability of choosing an imaging strategy as a function of the levels of the attributes. Results from the main effects model will be used to estimate the marginal willingness to accept an imaging strategy for each level of an attribute by looking at the ratios of the coefficients between an attribute level. Statistical significance from 0 for coefficients t will be assessed at p-value <0.05.

The survey will include an attention check to determine whether respondents will choose the correct alternative when one choice is clearly the same or better on all attribute levels. We will run sub-analyses that eliminate responses that failed the attention check twice.

No identifiable information will be provided via the Sawtooth survey. Therefore, risks of respondent's privacy being breached online will be minimal.

10. FACILITIES and PERFORMANCE SITES:

The proposed study will be performed at three sites – CCHMC, Mayo Clinic, and New York University Langone Health. CCHMC will be the lead site and serve as the Institutional Review Board of record for all participating sites. Clinical imaging will be performed using MRI scanners in approved clinical locations, while research imaging will be performed using dedicated research scanners that are FDA-cleared for clinical use and that are operated within appropriate safety limits.

11. POTENTIAL BENEFITS:

There are no direct study-related benefits. However, participants could benefit from our abbreviated research MRE protocol in the future, should it be determined to be non-inferior to conventional, standard of care MRE. The abbreviated MRE could be better tolerated, allow more frequent imaging, have shorter examination times, and have lower healthcare costs.

12. POTENTIAL RISKS, DISCOMFORTS, INCONVENIENCES AND PRECAUTIONS:

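### The sMaRIA comparison names the Mann-Whitney U test, which is for independent groups, although every participant contributes a pair of scores

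*Protocol*

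**What the plan says.** Protocol Section 9 plans that the global and segment "sMaRIA scores will be compared and correlated between clinical and research examinations using Mann-Whitney U tests and Spearman rank-order correlation". The comparison is additional to the primary analysis, which concerns the presence of moderate-severe inflammation.

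The design that produces these scores is described in three places:

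- **Pairing by participant.** Section 4 says participants will "undergo a dedicated research abbreviated MRE examination within ± 10 days of their clinical MRE". Section 8 repeats this.
- **Pairing by reader.** Section 8 says the radiologists "will independently review both the clinical standard-of-care and research abbreviated MRE examinations in separate sessions".
- **Size.** Section 6 says "Approximately one hundred participants will be enrolled and imaged at each site", and Section 10 says "The proposed study will be performed at three sites", which gives about 300 pairs.

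No section names a paired test for sMaRIA, a within-participant difference with a confidence interval, or any other allowance for the pairing.

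**The concern.** The sentence in Section 9 treats the data in two incompatible ways. Spearman correlation between the two examinations can be computed only on pairs. Mann-Whitney U treats the two sets of scores as coming from different people. Two examinations of the same bowel within 10 days should be positively correlated, and the unpaired test then uses too large a variance for the difference.

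This is the only named test of whether the abbreviated examination gives systematically higher or lower sMaRIA scores. Spearman cannot fill that role: adding a constant to every research score leaves it unchanged. Section 4 states "The proposed prospective investigation will be designed as a non-inferiority study", so the hoped-for result is that the two examinations agree. A test that under-detects differences makes an apparent absence of difference in severity scores easy to obtain.

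**Working it through.** The protocol gives no sMaRIA SD, correlation, relevant shift or power, so there is no planned figure to reproduce. The check asks how the named test behaves on paired scores.

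**Inputs**

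- From the protocol: n = 3 × about 100 = about 300 pairs (Sections 6 and 10).
- Assumed: two-sided alpha 0.05 (Section 9 gives p < 0.05 only for the choice-model coefficients), one score pair per participant, correlation ρ of 0.5–0.9, and shifts in SD units.

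**Type I error by approximation.** The unpaired test takes the variance of the mean difference as 2·SD²/n. The true variance is 2·SD²(1−ρ)/n. The actual type I error is therefore about 2[1 − Φ(1.96/√(1−ρ))]:

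- ρ = 0: 5.0%
- ρ = 0.3: 1.96/0.837 = 2.34, giving 1.9%
- ρ = 0.5: 1.96/0.707 = 2.77, giving 0.56%
- ρ = 0.7: 1.96/0.548 = 3.58, giving 0.035%

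**Shift detectable with 80% power by approximation.** Unpaired: (1.96 + 0.84√(1−ρ))·√(2/300). Paired: (1.96 + 0.84)·√(2(1−ρ)/300).

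| ρ | Unpaired (SD) | Paired (SD) |
|---|---|---|
| 0.5 | 0.209 | 0.162 |
| 0.7 | 0.198 | 0.125 |
| 0.8 | 0.191 | 0.102 |
| 0.9 | 0.182 | 0.072 |

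**Shift at which Mann-Whitney has 50% power, normal scores.** 1.96 / (√(3/π) × √(300/2)) = 1.96 / (0.977 × 12.25) = 0.164 SD, whatever ρ is.

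**Simulation, continuous score.** Bivariate normal, 300 pairs, 3,000 runs per cell. Each cell shows Mann-Whitney / signed-rank.

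| ρ | Type I error | Power, 0.10 SD | Power, 0.15 SD | Power, 0.20 SD |
|---|---|---|---|---|
| 0.5 | 0.6% / 4.6% | 14% / 40% | 42% / 72% | 73% / 92% |
| 0.7 | 0.1% / 4.7% | 9% / 59% | 39% / 91% | 78% / 99% |
| 0.8 | 0% / 5.2% | 5.5% / 75% | 37% / 98% | 82% / 100% |
| 0.9 | 0% / 5.2% | 1% / 97% | 32% / 100% | 90% / 100% |

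At 0.30 SD both tests reach 99–100%. A separate simulation with 1,500 runs per setting gave the same pattern at zero shift, 0.10 SD and 0.15 SD.

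**Simulation, coarse scores.** Shifts here are in SDs of the underlying normal variable, ρ = 0.5–0.9.

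- Integer score floored at zero: Mann-Whitney type I error 0–1.2%; power 3–13% against 29–78% for signed-rank at 0.10 SD, and 59–65% against 80–100% at 0.20 SD.
- 0–5 score with about 60% zeros: at 0.10 SD, 11% against 25% (ρ = 0.5) and 2% against 72% (ρ = 0.9).
- Segment-type score with about 80% zeros: Mann-Whitney power only about 40–44% at 0.20 SD.

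**If reads were pooled.** The protocol does not say that several readers' scores would be entered as independent observations, and it gives no reader count. Under three assumed sets of variance shares (participant, examination, participant-by-reader, residual), type I error was:

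| Analysis | 3 readers | 6 readers |
|---|---|---|
| Mann-Whitney on pooled reads | 1.3–5.4% | 6.6–15% |
| Signed-rank on pooled reads | 15–21% | 30–36% |

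Signed-rank on each participant's reader-mean difference kept it at 4.8–5.4%. This bears on how the correction is worded: changing the test name alone would not be safe if reads are combined.

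**The case against.** The strongest reply concerns weight. With one positively correlated pair per participant the test errs on the cautious side and produces fewer false positives than 5%. No decision rule rests on the sMaRIA p-value. A shift large enough to cross the moderate-severe threshold would also show as lower sensitivity or specificity, which Section 9 analyses at examination and segment level. The loss is concentrated in small shifts, and nothing in the protocol shows that shifts of 0.10–0.20 SD matter clinically. Nor does it say that a non-significant result will be read as agreement. Confidence intervals and handling of multiple readers are details that an analysis plan commonly supplies.

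Much of this is fair. The fault is conservative in the single-reader case, the analysis is secondary, misreading the result is a risk and not a stated intention, and the upward error under pooling is conditional on something the protocol does not state. None of it makes Mann-Whitney suitable for paired scores. An unseen analysis plan does not remove the problem either: Section 9 itself names the test, so a plan naming a paired test would contradict it.

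One further point cuts the other way. The 0.164 SD figure and the good power at 0.20 SD belong to a continuous normal score. On coarse, zero-heavy scores, which segment scores may resemble, Mann-Whitney does worse than those figures suggest. The advantage of pairing can also be smaller there when the correlation is only 0.5.

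**Conclusion.** The concern holds. Section 9 names an independent-samples test for paired scores, and nothing else in the protocol corrects it. For a single-reader analysis of about 300 pairs and a continuous score, Mann-Whitney would more often than not miss a systematic shift below about 0.16 SD. A paired test finds such shifts far more often: at 0.15 SD, 72–100% against 32–42%. Coarser scores show the same direction.

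The sizes rest on the assumed correlation, score shape and shift, none of which the protocol gives. At zero correlation the two tests perform alike. That the test does not fit the design needs only that the two scores of one participant are correlated.

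This should be fixed, but it does not touch the primary sensitivity and specificity analysis. What is at stake is the reading of the severity scores: as planned, a non-significant test beside a high Spearman correlation would say little about whether the two examinations score alike.

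**What to change.** In Section 9:

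1. Replace the Mann-Whitney U test with the Wilcoxon signed-rank test on within-participant differences (research minus clinical), per reader, for the global score and for each bowel segment separately.
2. Report the paired difference with its 95% CI beside the Spearman correlation.
3. Where readers or segments are combined, use a paired analysis that respects clustering by participant, for example by averaging the differences within each participant before testing. A plain signed-rank test on pooled reads is not enough.
4. State that a non-significant result will not be read as equivalence of the scores.

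The cost is one or two sentences. No new data, visits or reads are needed.
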